1.4.2 Molecular Interference Screening with JAK loss of function cell lines

To perform a molecular interference screening analysis of target tumor cell lines including ATL, Lymphoid Malignancies Branch laboratory investigators led by [name] have created a library of retroviral vectors for inducible expression of small hairpin RNAs (shRNAs)³⁵. A critical feature of this system is the inclusion of a 60-base pair molecular barcode in each vector which allows the abundance of each vector to be monitored in a population of transduced cells. This extensive shRNA library contains 11,274 vectors that targets 3,033 human genes and can be used to assess therapeutic potential of molecular therapeutics. Using this inducible shRNA library, a loss-of-function genetic screen, half of the cultures were induced to express shRNA and half served as the control to assess the consequence of depleting essential genes in the intended treatment population. Relative abundance of shRNAs is monitored by their unique barcodes using microarray and the relative amount of shRNA indicates how much “interference” was required to suppress the target gene. When this screen was applied to three distinct ATL cell lines, JAK1 was shown to be critical in the proliferation and survival of the six of the seven cell lines studied ([Figure 7](#)) adding support to the notion that JAK signaling is critical in ATL and an appropriate therapeutic target.

[figure not shown]

Figure 7: Using an inducible shRNA for JAK1 a loss of function screen applied to seven distinct ATL cell lines JAK1 was shown to be critical in the proliferation and survival of six of seven lines studied.

1.4.3 In Vitro Matrix screening assessment

Preliminary results from matrix high-throughput screening for cellular signaling analyses directed at known targets and pathways showed that a JAK1/2 inhibitor inhibited the proliferation and survival of the 5 ATL cell lines tested with LD50s of 1.6 uM, 5.1 uM, 8.1 uM, 18.7 uM and 25.6 uM. Taken as a whole, these preclinical studies have demonstrated the importance of the JAK1 and 3 signaling elements in ATL lymphocytes, the ability of current clinical agents to inhibit pathophysiologic IL-2, IL-9 and IL-15 driven stimulation in ATL and strongly support a clinical trial evaluating the JAK1 inhibitor ruxolitinib for the treatment of patients with smoldering or chronic ATL.

1.5 CLINICAL EXPERIENCE WITH RUXOLITINIB

1.5.1 Pharmacokinetics (PK) and Pharmacodynamics (PD) of Ruxolitinib

The Janus-associated kinases 1 and 2 mediate the signaling of a number of cytokines and growth factors that are important for hematopoiesis and immune function. Absorption, distribution, metabolism and excretion (ADME) and pharmacokinetic studies performed to support the licensing application for ruxolitinib showed rapid and near complete absorption (95%) after administration with maximum plasma concentration (C_{max}) of 1.47 μ M achieved within 1 to 2 hours post dose. The mean C_{max} and total exposure (AUC) of ruxolitinib increased proportionately over the (single) dose range of 50 to 200 mg. The apparent volume of distribution of ruxolitinib at steady state is 53 to 65 L with high protein binding (97%) that is mostly to albumin. Ruxolitinib administration resulted in maximum inhibition of STATs phosphorylation 2 hours after dosing with return to near baseline by 10 hours in both healthy subjects and myelofibrosis patients. CYP3A4 is the major enzyme responsible for the metabolism of ruxolitinib. Following a single dose of [^{14}C]-labeled ruxolitinib in healthy adult subjects, elimination was predominantly through metabolism with 74% of radioactivity excreted in urine and 22% via feces³⁶.

1.5.2 Ruxolitinib Clinical Trial Results

Several Phase 1, 2 studies and two randomized Phase 3 studies (studies 1 and 2) were conducted in patients with myelofibrosis (MF) (either primary myelofibrosis, post-polycythemia Vera myelofibrosis [PV] or post-essential thrombocytopenia-myelofibrosis [ET])^(36, 37). Patients with a platelet count $> 200 \times 10^9/L$ were started on ruxolitinib orally 20 mg twice daily. In the 155 MF patients receiving ruxolitinib there was a 35% reduction in spleen volume in 65 (41.9%), as compared to one (0.7%) in the 154 patients in the placebo group. 148 patients receiving ruxolitinib achieved $\geq 50\%$ improvement from baseline in the total symptoms score, in contrast to 8 of 152 patients 5.3% in the placebo-control group^{36, 37}. The safety data base in solid tumors and hematologic malignancies consisted of 787 patients treated with ruxolitinib in 6 studies evaluating patients with MF (N=679), prostate cancer (N=22), multiple myeloma (N=13), ET and PV (N=73), of whom 617 patients received ruxolitinib. Hematologic events were the most frequently reported adverse events (AEs) primarily thrombocytopenia and anemia. The majority of these AEs are grade 1-2 and seldom led to drug discontinuation (<1% of patients). Of the 155 patients who received ruxolitinib in study one 10 (6.5%) had grade 3 thrombocytopenia and one (0.6%) had grade 4 thrombocytopenia as contrasted with one and 0 patients in the placebo group. Ten patients had grade 3 and 6 patients had grade 4 anemia compared to 5 and 0 in the placebo group. Biochemistry abnormalities of alanine aminotransferase (ALT), aspartate aminotransferase (AST) and cholesterol were also reported and again the majority of these increases were grade 1 or 2 with no grade 4 observed. In this study there were 9 deaths in the ruxolitinib group and 11 in the placebo group. The safety data base which is primarily from patients with an underlying

hematopoietic production defect indicates a well-tolerated drug that did cause additional decreases in blood elements.

1.5.3 Summary of Adverse Events

Table 2: Adverse Reactions Occurring in Patients on the Phase III MF Trial

Adverse Reaction*	Ruxolitinib (N=155)			Placebo (N=151)		
	All Grades (%)	Grade 3 (%)	Grade 4 (%)	All Grades (%)	Grade 3 (%)	Grade 4 (%)
Bruising	23.2	0.6	0	14.6	0	0
Dizziness	18.1	0.6	0	7.3	0	0
Headache	14.8	0	0	5.3	0	0
Urinary Tract Infections	9.0	0	0	5.3	0.7	0.7
Weight Gain	7.1	0.6	0	1.3	0.7	0
Flatulence	5.2	0	0	0.7	0	0
Herpes Zoster	1.9	0	0	0.7	0	0

*CTCAE version 3

Table 3: Worst Hematology Laboratory Abnormalities in Patients on the Phase III MF Trial

Laboratory Parameter	Ruxolitinib (N=155)			Placebo (N=151)		
	All Grades (%)	Grade 3 (%)	Grade 4 (%)	All Grades (%)	Grade 3 (%)	Grade 4 (%)
Thrombocytopenia	69.7	9.0	3.9	30.5	1.3	0
Anemia	96.1	34.2	11.0	86.8	15.9	3.3
Neutropenia	18.7	5.2	1.9	4.0	0.7	1.3

1.6 RATIONALE FOR PATIENT SELECTION, CHANGE IN THE TREATMENT SCHEDULE AND TARGET RESPONSE RATE IN THE INITIAL PHASE II TRIAL

1.6.1 Preclinical Experiments

Eligibility for entry into the present trial is limited to patients with smoldering or chronic ATL since the ex vivo PBMCs containing ATL cells from such patients proliferated spontaneously and this proliferation was inhibited by the addition of ruxolitinib. Furthermore, the survival and proliferation of cytokine-dependent ATL cell lines were inhibited by the addition of ruxolitinib or shRNA for JAK1—a target of ruxolitinib. In contrast the ex vivo PBMCs from patients with acute and lymphomatous ATL did not proliferate spontaneously. Furthermore, the survival of cytokine-independent ATL cell lines was not inhibited by the addition of ruxolitinib or by the addition of a shRNA for JAK1. Although the Shimoyama Classification⁵ System is valuable and generally accurate, there are patients who are not easily assigned to a subtype. This problem is most apparent in patients considered the chronic type, since chronic subtype patients can have lymphadenopathy, hepatomegaly and splenomegaly that are key criteria for the lymphomatous subtype patients. A key distinction that separates chronic from lymphomatous subtype is that chronic patients have an elevated absolute lymphocyte count with circulating ATL cells whereas lymphomatous patients have no evidence of leukemic involvement.

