2 ELIGIBILITY ASSESSMENT AND ENROLLMENT

2.1 ELIGIBILITY CRITERIA

2.1.1 Inclusion Criteria

NOTE: After approval and activation of Amendment D, patients who have failed this protocol treatment previously at the initial dose level may be eligible for re-enrollment and retreatment if they otherwise meet eligibility criteria.

- 2.1.1.1 Patients \geq 18 years old with pathologically confirmed adult T- cell leukemia: smoldering or chronic, or previously treated lymphomatous or acute subtypes with clinically indolent behavior indicated by lack of significant symptoms and treatment free interval of greater than 6 months are eligible for treatment in the dose escalation and expansion cohorts (see also [APPENDIX B](#)).
- 2.1.1.2 Patients must have serum antibodies directed to HTLV-1.
- 2.1.1.3 Patients must have measurable or evaluable disease. Patients with $> 10\%$ of the PBMCs having the characteristic abnormal (i.e., $CD3^{\text{dim}}$, $CD4^+$ $CD25^+$ expressing) FACS profile for circulating ATL cells will be considered to have evaluable disease.
- 2.1.1.4 Patients must have adequate physiologic parameters:
 - Absolute granulocyte count \geq 500 K/uL, platelet count \geq 75,000 K/uL and hemoglobin \geq 10 g/dL.
 - Bilirubin and creatinine \leq 1.5 x institutional ULN.
 - AST, ALT \leq 3.0 x institutional ULN.
- 2.1.1.5 Karnofsky Performance Score \geq 70% or ECOG \leq 1 ([APPENDIX A](#)).
- 2.1.1.6 Patients must be able to understand and sign Informed Consent Form.

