Updated Study Design (Amendment D): Although there were 4 responding patients in the first 12 patient who were treated, the activity was not sustained even in these patients; therefore, we are now changing the treatment regimen to evaluate the activity of augmented dosing (effective with Amendment D). We plan to treat a total of 9 patients at the MTD or MAD and will not proceed with the same original two-stage phase 2 dosing. Patients who discontinue treatment within the first 28 days for reasons other than toxicity will be considered inevaluable. In order to allow for this assessment of patients attempting higher treatment doses, the protocol will require an additional 15-21 patients. Accounting for the previously enrolled 12 subjects, the new design, and to assess up to 9 patients for response at the MTD/MAD level with the new increased dose levels as well as allowing for up to two (2) inevaluable patients: the new accrual ceiling will be set at 35 patients.

The major objective of this study continues to be to determine the antitumor activity of ruxolitinib with regard to response rate and time to progression. Response rate will be based on the number of patients who achieve either a complete or partial response to therapy. Time to progression will be measured from the date of registration until documentation of disease progression..

An exploratory analysis will be performed in the two subgroups of patients defined by the inhibition of their pretreatment *in vitro* ATL cells proliferation by ruxolitinib treatment. The patients will be distinguished on the basis of the results of a 6-day *ex vivo* culture analyses performed on patient peripheral blood mononuclear cells prior to drug administration. One subgroup of patients will be defined as those who fulfill the following criteria: peripheral blood mononuclear cells proliferate *ex vivo* ($\geq 5,000$ CPM/1 μ C) in 6-day culture and their thymidine uptake must be reduced by 40% by the addition of 10 μ M ruxolitinib. The other group of patients would be all the remaining treated patients that do not fulfill these criteria. Since a limited number of patient samples have been assessed to date, it is not clear what percentage of smoldering or chronic stage ATL patients will fulfill the criteria for group 1.

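### Section 8's exploratory subgroup rule pools resistant, non-proliferating and unassayed patients in one group, so the comparison may partly reflect ATL subtype and not ruxolitinib sensitivity

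*Combined protocol and SAP*

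**What the plan says.** Under Amendment D, Section 8 states: "An exploratory analysis will be performed in the two subgroups of patients defined by the inhibition of their pretreatment" in vitro proliferation. Membership of group 1 has two conditions.

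- Proliferation: "One subgroup of patients will be defined as those who fulfill the following criteria: peripheral blood mononuclear cells proliferate" ex vivo, at 5,000 CPM or more, in a 6-day culture.
- Inhibition: "their thymidine uptake must be reduced by 40% by the addition of 10" µM ruxolitinib.

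Group 2 is defined by exclusion: "The other group of patients would be all the remaining treated patients that do not fulfill these criteria". On the expected split, Section 8 says only that "it is not clear what percentage of smoldering or chronic stage ATL patients will fulfill the criteria for group 1".

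Three other places bear on who lands in group 2.

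- **Assay behaviour by subtype (1.6.1).** Smoldering and chronic PBMCs proliferated and were inhibited. For the other subtypes: "In contrast the ex vivo PBMCs from patients with acute and lymphomatous ATL did not proliferate spontaneously". The same section separates chronic from lymphomatous disease by an elevated lymphocyte count with circulating ATL cells, "whereas lymphomatous patients have no evidence of leukemic involvement".
- **Eligibility (2.1.1.1).** Besides smoldering and chronic disease, the trial admits "previously treated lymphomatous or acute subtypes with clinically indolent behavior". The primary objective (1.1.1) and the design section (3.1) agree.
- **Assay availability (3.5 footnote 13 and 5.1.2).** The proliferation assay is optional, at the investigator's discretion, and is not run when there are too few lymphocytes.

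**The concern.** The two groups are labelled by drug inhibition, so a reader will take group 2 to mean not sensitive. Only some of its members will have been shown to be so. If acute and lymphomatous patients gather in group 2 and respond less often for reasons unrelated to the assay, group 1 will show the higher response rate even when the assay predicts nothing. The trial could then report a promising selection marker that partly restates the subtype known at enrolment.

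Unassayed patients add a second distortion. They carry no information on sensitivity, yet they count as not meeting the criteria. Because low lymphocyte counts are one reason for not running the assay, they are not a random sample of the treated patients.

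**Working it through.** The plan gives no sample size, expected difference or test for this comparison, so there is no figure to reproduce. The check has two parts.

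**1. Applying the rule to each kind of patient**

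| Patient | Proliferates? | Inhibition measured? | Group |
|---|---|---|---|
| Grows, inhibited by 40% | yes | yes | 1 |
| Grows, not inhibited | yes | yes | 2 |
| Does not reach 5,000 CPM | no | no | 2 |
| Not assayed | unknown | no | 2 |

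Only the second row is measured resistance. If eligible acute and lymphomatous patients behave in the assay as 1.6.1 describes, they fall in the third row. Section 8 does not restrict, stratify or adjust by subtype, and does not separate the last three rows.

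**2. Size of the gap when the assay predicts nothing**

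Inputs:

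- N = 21 new patients, the top of the 15 to 21 in Section 8.
- pC = 0.33, response in smoldering and chronic patients. This borrows the 4 of 12 seen at 20 mg (1.6.3), which is not broken down by subtype.
- nA, the number of acute and lymphomatous patients: assumed 3 to 9. nC = 21 − nA.
- pA, their response rate: assumed 0.05 to 0.20.
- f, the share of smoldering and chronic patients meeting group 1: assumed 0.5 to 0.7.
- All acute and lymphomatous patients fall in group 2, and response is the same within a subtype whatever the assay shows.

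Group 1 rate = pC.

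Group 2 rate = [nC(1 − f)pC + nA·pA] / [nC(1 − f) + nA].

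Gap = nA(pC − pA) / [nC(1 − f) + nA].

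Results:

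- Middle case (nA = 6, f = 0.7, pA = 0.10): 6 × 0.23 / (15 × 0.3 + 6) = 1.38 / 10.5 = 0.131, that is 33% against 19.9%, a ratio of 1.7.
- Smallest (nA = 3, f = 0.5, pA = 0.20): 3 × 0.13 / (18 × 0.5 + 3) = 0.39 / 12 = 0.03.
- Largest (nA = 9, f = 0.7, pA = 0.05): 9 × 0.28 / (12 × 0.3 + 9) = 2.52 / 12.6 = 0.20.
- nA = 0 or pA = pC: gap 0.

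A second set of assumptions, with the 30% target rate of Section 8 in place of 33%, gives similar values. Take a quarter of patients acute or lymphomatous and f = 0.8. With pA = 0.05, group 2 responds at (0.25 × 0.05 + 0.75 × 0.2 × 0.30) / (0.25 + 0.15) = 0.144, a gap of 15.6 points. With pA = 0.15 the gap is 9.4 points.

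For scale, the middle case has 10.5 patients per group. The standard error of the difference is √(0.33 × 0.67 / 10.5 + 0.199 × 0.801 / 10.5) = 0.19. The artefact is thus smaller than the sampling error, at about 1.4 responders (3.5 against 2.1).

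**The case against.** A reader might infer that acute and lymphomatous patients are placed in group 2 by construction. The documents do not support that. The rule is a CPM threshold and does not mention subtype. The statement in 1.6.1 gives no number of samples and no cut-off, and it describes these subtypes in general. Those eligible here are previously treated, clinically indolent and more than six months off treatment, and 1.6.2 says such disease can behave like the indolent subtypes. That remark concerns clinical course; no ex vivo data are given for these patients either way. Nor does the argument that the assay samples few tumour cells extend to acute ATL, which is leukemic. Likely placement is as far as the text goes.

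A reader might also infer that the assay merely re-labels subtype. That too goes further than the text. Section 1.6.1 offers spontaneous proliferation as the reason for choosing smoldering and chronic patients, and reports that cytokine-independent lines were not inhibited. Failure to proliferate may itself mark insensitivity, and subtype may lie on the same biological path. This is a fair reason to keep non-proliferators in view. It does not justify merging them with measured resistance, because the pooled group cannot show which explanation applies.

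The 4-year survival figures by subtype in 1.2.4.1 are no evidence of a lower response rate here: they are survival, and they come from newly diagnosed patients not selected for indolent behaviour.

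It can also be said that the trial enrols only smoldering and chronic disease. The opening of 1.6.1 says so, and Section 8 promises strict use of those two definitions. Both conflict with 1.1.1, 2.1.1.1 and 3.1. If the narrower text governed, the subtype problem would go, but the pooling of unmeasured with resistant patients would remain.

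Finally, the analysis is exploratory, with no test or decision attached. That stands, and it limits the weight of the point.

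**Conclusion.** The point holds as a defect in the definition of group 2. The rule combines measured resistance, unmeasurable inhibition and missing assays. On the protocol's own account of the assay, it is likely to concentrate acute and lymphomatous patients in that group, so the comparison may partly reflect subtype.

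The size cannot be established from the documents. The range of about 3 to 20 points rests on an assumed subtype mix, assumed response rates, an assumed share meeting group 1, and the 4 of 12 result used as if it applied to smoldering and chronic patients alone. With numbers this small, chance would outweigh the artefact in any single result.

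This is a cheap improvement to an exploratory analysis. It does not touch the MTD or the overall response rate.

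**What to change.** Rewrite the exploratory paragraph of Section 8 as follows.

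- **Comparison.** Among assayed smoldering and chronic patients whose PBMCs reach 5,000 CPM, compare those inhibited by at least 40% with those not inhibited.
- **Separate descriptive rows.** Report non-proliferators, unassayed patients, and acute and lymphomatous patients each on their own, with response by subtype.
- **No extra restriction on circulating cells.** The more-than-10% figure in 2.1.1.3 defines evaluable disease and is not given as a limit on assay validity. Appendix B allows smoldering disease at 5% abnormal cells, or fewer with a histology-proven lesion, so using it here would drop eligible target patients.

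Reconcile the smoldering-and-chronic-only statements in 1.6.1 and Section 8 with 1.1.1, 2.1.1.1 and 3.1, so that it is clear which subtypes the analysis covers.

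The cost is one paragraph and no new data. The comparison will have fewer patients, and the not-inhibited group may be very small; the separate rows keep everyone visible in the report.

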1.6.2 Results of Standard Treatment for ATL

Many of the Lymphoid Malignancies Branch chronic subtype patients will have received prior chemotherapy. Their classification will be determined on their status when they are being considered for ruxolitinib therapy rather than that at their initial presentation. While the Shimoyama classification system generally separates patients into the biologically indolent subtypes (smoldering and chronic) and the more aggressive subtypes (lymphomatous and acute), ATL is a highly variable disease and unusually poorer prognosis lymphomatous or acute subtype patients can have durable symptom free intervals following standard treatment where their disease behaves more like the indolent subtype. We believe it is appropriate to consider these patients for treatment on this protocol when there is clear evidence their ATL is quiescent and does not require urgent treatment for symptomatic progressive disease.

As noted above, there is data to suggest that the response rates to IFN and AZT in previously treated ATL patients was much lower (18% and 26%) in two reports than the response rates for treatment of naïve patients ^{42, 43}. Recently this resistance to AZT/IFN therapy has been demonstrated to be associated with P53 mutation and elevated IRF4 and cRel levels in the ATL cells of previously treated patients ^{44,45}. In the initial report by Shimoyama and coworkers, patients with chronic ATL had a median survival duration of 24.3 months. Patients with chronic ATL and adverse disease characteristics such as poorer performance status, lower neutrophil count and receive chemotherapy have poorer median survival compared to other chronic subtype patients and is reflected in the 47% 5-year survival rate noted in this long term follow up of “indolent” ATL patients ⁴⁶. Since duration of benefit is important in the treatment of chronic diseases such as chronic and smoldering ATL, survival is the clinical endpoint most often captured in these treatment reports. Response rates are frequently not sited and survival data can be difficult to compare in reports of different clinical trials based on the type of “chronic” ATL patients enrolled. One Japanese study reported a 4-year OS rate of 26.9% in patients managed with watchful waiting and then chemotherapy ⁴⁷ that is very different than the survival data sited in the Journal of Clinical Oncology “Meta- analysis.” The Takahashi review⁴⁶ indicates heavily pretreated patients further along in the natural history of their ATL respond less well to any form of treatment and initial target response rate of 30% in our referral patient population is an appropriate target value for response in a phase II trial⁴¹

1.6.3 Early Experience in this Trial

The initial 12 patients enrolled in the trial were treated with the standard 20 mg dose twice daily of off label ruxolitinib and tolerated the drug with little if any side effects, but responses were seen in only 4 of these patients. Three of these patients had more than a 50% decrease in the volume of their skin involvement and the other patient had 50% improvement in the number of circulating ATL cells, but the duration of these responses were 2 to 6 months. Serial analysis of phosphoSTAT 3 and phosphoSTAT5 on patients’ samples after treatment showed only transient inhibition of the phosphorylation of STAT 5 in the immediate post-treatment period. These results are consistent with the *ex vivo* inhibition experiments performed with ruxolitinib at the 1 and 10 μ M concentrations and ruxolitinib’s known pharmacokinetics (Cmax of 1.47 μ M \approx 2 hours post dose and terminal elimination $t_{1/2}$ of \approx 3 hours) resulting in a transient inhibition of the JAK-STAT signaling pathway that is marginally clinically active.

[figure not shown]
[figure not shown]

Figure 8: Effect of ruxolitinib on the endogenous phosphorylation of STAT3 and STAT 5 in ATL cells (ex vivo PBMCs isolated after oral ruxolitinib 20mg)

